Overview of Autism Spectrum Disorder	5
Standard of Care – Treatment of Autism Spectrum Disorder & Barriers	5
1 Study Device Description	8
2 Study Objectives	9
2.1 Study Purpose	9
3 Study Outcome Measures	9
4 Study Duration	9
5 Study Population	10
5.1 Study participant Recruitment and Selection	10
5.2 Inclusion Criteria:	10
5.3 Exclusion Criteria:	10
6 Study Assessment	10
6.1 Training	11
6.2 Usability Metrics	11
7 Data Collection and Storage	12
8 Adverse Events	12
8.2 Recording AEs/ADEs and SAEs/SADEs	13
8.3 Follow-up of participants after AEs	14
9 Potential Risks/Benefits	14
10 Study Management and Administrative Considerations	15
10.1 Informed Consent	15
10.2 Participant Confidentiality	15
10.3 Financial Considerations	16
10.4 Study Discontinuation	16
References	16

Protocol Summary

Title	Cognoa ASD digital therapeutic engagement and usability study
Objective	To assess the usability and efficacy of the device.
Study Design	Single-arm prospective interventional study
Enrollment	Up to 30 participants
Outcome Measures	Change in scores on the Vineland-3 domain level caregiver report social skills and relationships Measures of Usability
Subject Population	Caregivers and female and male participants between the ages \geq 3 years and $<$ 9 years of age on date of enrollment from a general population diagnosed with ASD
Planned Schedule	Enrollment, baseline assessment, 4 weeks of intervention 4-6 times a week, weekly surveys of usability, final assessment.

Overview of Autism Spectrum Disorder

Autism Spectrum Disorder (ASD) is a neurodevelopmental disorder that affects socialization, communication and behavior. According to the Diagnostic and Statistical Manual of Mental Disorders, Fifth Edition (DSM-5), a guide created by the American Psychiatric Association and used by health-care professionals (HCPs) to diagnose mental disorders, ASD primarily consists of persistent deficits in social communication and social interaction as well as the presence of restricted, repetitive patterns of behaviors, interests, and/or activities that can persist throughout life.

ASD is said to be a “developmental disorder” because symptoms generally appear in the first two years of life and is known as a “spectrum” because there is a wide variation in the type and severity of symptoms people experience. Symptoms can include lack of joint attention, poor eye contact, difficulty reading social cues and facial expressions, failure to develop peer relationships, lack of social or emotional reciprocity, delayed speech development, difficulty sustaining conversations, lack of make-believe play, repetitive motor mannerisms, rigid adherence to routines, restricted interests and hyper- and/or hypo sensitivity to sensory input.

ASD can have a significant impact on a child’s day-to-day functioning including but not limited to impairments in communicating and getting needs met as well as difficulties with activities of daily living such as eating, dressing, playing, and sleeping. Most studies related to comorbidities in ASD have shown increased rates of anxiety and attentional disorders, when left untreated, reflecting cognitive, language, and social problems (Leyfer, Folstein, Bacalman, et al., 2006).

Caregivers are also greatly impacted with higher rates of stress, depression, anxiety, and other mental health disorders than in parents of children with other developmental delays and disabilities (Dumas, Wolf, et al., 1991; Hayes & Watson, 2013).

Standard of Care – Treatment of Autism Spectrum Disorder & Barriers

Reciprocal social behavior, a foundational capacity to engage in contingent social interactions important for learning and relationships, is typically disrupted in autism spectrum disorder (ASD). If unaddressed, the social deficits experienced by individuals with ASD can lead to lifelong struggles and a disabling condition. The National Institute of Mental Health (NIMH Report to Congress) and Interagency Autism Coordinating Committee (IACC Portfolio Analysis Report) identified the development of interventions to address social impairment in individuals with autism as a high priority. Individuals with ASD typically have few friends and experience loneliness due to difficulties recognizing subtle social cues and emotional states in others (Bauminger et al., 1999). ASD individuals who have social communication difficulties have significant challenges with the ability to form and maintain relationships. Without appropriate effective

intervention, therefore, ASD can result in loneliness, isolation, and an increased risk of depression and suicide (Hedley and Uljarevic, 2018). As such, developing friendships is recognized as one of the top goals of children, adolescents, and adults with ASD (Orsmond et al., 2004).

There is no cure for Autism. Interventions consist in treating symptoms, to reduce their severity and improve behavioral, social, emotional, and cognitive functioning. They include intensive behavioral interventions, rehabilitative services such as speech therapy, occupational therapy, physical therapy, social skills training, and counseling. Traditional pharmacotherapy may also be used to treat symptoms in ASD patients (e.g irritability, aggression) but does not affect the core symptoms of ASD (Choueiri & Zimmerman, 2017).

Among all children with an ASD diagnosis, 64% had received behavioral therapy in the past 12 months while 27% used medication to ease the symptoms (Zuckerman et al, 2017). No current medical intervention demonstrates clear benefit for social or communication symptoms in ASDs other than behavioral therapy approaches (however, 2 recent studies have concluded that standard behavioral therapy assessed in RCTs do not show effect). Furthermore, there are no currently FDA approved pharmacotherapies indicated for use to treat the core symptoms of ASD directly. Psychotropics are sometimes prescribed for irritability, such as risperidone and aripiprazole, especially in children who received an ASD diagnosis at older ages (Ji & Findling, 2016; Zuckerman, Lindly, & Chavez, 2017). Monitoring guidelines for these medications, due to possible side effects, include monitoring weight, height, and body mass index, extrapyramidal symptom screening, blood pressure, abdominal girth and liver enzymes, fasting plasma glucose, and fasting lipids. Adherence to monitoring for all measures in one study was only 20% (Jawaheri et al., 2019). Intranasal oxytocin has shown some potential for improving some aspects of social functioning such as emotion recognition and eye gaze (Prete et al., 2014). Although FDA granted Roche Breakthrough Therapy designation in 2018 for its Balovaptan product (selective small molecule antagonist of the vasopressin V1A receptor), it remains in Phase III.

The current standard of care for treating socialization difficulties in children with ASD is behavioral therapy, and most prominently a therapy called Applied Behavioral Analysis (ABA) (Lovaas, 2003). ABA relies on teaching social skills in clinical sessions, via tools such as flashcards involving memorization of facial emotions (**Figure 1**) (Landa et al., 2011 and Lerman et al., 2004). Severity of autism is also associated with higher rates of behavioral interventions, whereas only one in four children with mild ASD received any intervention.

ABA therapy is delivered both in the home as well as via clinic-based services, depending on a myriad of factors such as child age, availability of therapists, cost, transportation and logistics concerns, and treatment model of the provider. Parent and family participation and engagement outside of treatment hours, however, is consistently recognized as positively contributing to successful outcomes in children.

Greater parental involvement during treatments that fit into natural everyday routines not only increase the effectiveness of interventions but also improves parents' sense of self-efficacy and reduces their levels of stress (Hastings and Symes 2002; Moes 1995; Koegel et al. 1996a).

Figure 1. Flashcard examples used in ABA therapy today.

Experts recommend 20 hours per week of Applied Behavioral Analysis with a behavioral therapist for at least two years (Mazurek et al., 2014). Although ABA therapy can be effective in increasing IQ, improving eye contact, face-to-face gaze, and emotion recognition, children who receive ABA often struggle to generalize learned behaviors to natural interactions and are dependent on prompts (Lovaas et al., 1987). That is to say, they may perform better at emotional recognition and corresponding tasks in the same environment with a therapist, but may not perform as well outside of the controlled environment.

1 Study Device Description

The study device is an investigational digital therapy that uses Augmented Reality-based social behavioral therapy, as an adjunct to standard outpatient applied behavioral analysis therapy, to improve adaptive behavior, specifically social skills in children with Autism Spectrum Disorder.

The Device is a smart device (smartphone)-based therapy aid for children with ASD to encourage facial engagement, emotion recognition, and provide real-time feedback (via cues) to the child during social interactions at home. The intervention is provided to the child via a mobile application that is centered around a Facial Expression Recognition Activity (FERA), powered by machine-learning, and an Emotions Guessing Game (EGG); these two steps provide the main therapeutic mechanisms of action. The application is engaging and provides a regimented therapy administration to improve outcomes associated with socialization domains in Autism Spectrum Disorder.

The Device is a SaMD-based system comprising:

- A caregiver and child-facing smartphone mobile application (“app”) that provides the therapeutic content, including the FERA and EGG, instructions and other functions, using the smartphone camera for interactive activities in the therapy (primarily for the FERA)
- An underlying machine-learning engine for the FERA that drives the emotional recognition cue element of the therapy (explained further below).
- Several supporting software and backend services and infrastructure, including privacy and security encryption and infrastructure in compliance with HIPAA and other best practices for data security.

The Facial Expression Recognition Activity (FERA): the caregiver moderates the session, wherein the child aims the smartphone at the caregiver or other familiar adult within their natural and familiar environments (namely their own home or that of their extended family and friends), and either “finds” or tries to elicit 1 of several emotions that is prompted by audio in-app. Often, in the home setting, the emotion will be generated by the caregiver; the instructions to the caregiver will be to replicate the requested emotion or, during use of the Device in areas with multiple people, the

caregiver will be instructed to help the child find individuals expressing the prompted emotion; if none exist, the caregiver may choose to replicate the emotion (similar to EGG, described below) or prompt another individual in close proximity to replicate the emotion without alerting the child. The child points the phone camera towards the individual who they believe is expressing the prompted emotion; the mobile app has an Augmented Reality (AR) component that alerts the child when a face is detected. The screen then provides the child real-time audio and visual feedback correctly labeling the emotional expression displayed on the face.

The Emotional Guessing Game Activity (EGG): after the FERA activity is completed, the caregiver and child enters the EGG component of the application. The EGG stores previous images that the child has evaluated -- for example, the expressive faces successfully discovered during the FERA activities -- mixed with stock face images (from pre-reviewed sources). The goal of this activity is to reinforce and remind the child of their correct choices to improve retention. The child can then try to correctly match or label the emotional expressions displayed in the images. The goal from this EGG is to provide a bridge between FERA sessions that reinforces the learnings from the AR-based FERA in a different, 2D environment. It also provides additional social interaction opportunities between caregiver and child to review and discuss the emotions together.

2 Study Objectives

Cognoa will measure usability, engagement with the device, and changes in parent-reported socialization during a 4-week period of intervention at home with the Cognoa ASD therapeutic device.

2.1 Study Purpose

The purpose of this study is to evaluate the safety, effectiveness and usability of the device smartphone application, and Quick Start Guide) with intended users.

3 Study Outcome Measures

- Usability assessment of Cognoa ASD Therapeutic Device
- Change in scores on the Vineland-3 domain level caregiver report social skills and relationships from baseline to 4 week measurement

4 Study Duration

Duration of subject participation is approximately 4 weeks.

Total study duration is approximately 12 weeks.

5 Study Population

5.1 Study participant Recruitment and Selection

Up to 30 caregivers and children diagnosed with ASD ages ≥ 3 to < 9 years of age will be recruited from across the U.S.

Only subjects who meet all eligibility criteria will be enrolled into the study. Eligibility will be determined during a scheduled phone call by Cognoa recruiters.

5.2 Inclusion Criteria:

- Functional English language capability in the home environment.
- Parent, Guardian, or legal authorized representative (LAR) must be able to read, understand and sign the Informed Consent Form (ICF)
- Female or Male, ≥ 3 to < 9 years of age and parent/caregiver
- Diagnosis of Autism Spectrum Disorder
- Parent, Guardian, or legal authorized representative (LAR) must have smartphone capabilities for downloading Testflight software to access the Cognoa for Child development app; and the Cognoa Digital Therapeutic app (iOS 12.0 and up and Apple iPhone 8 and higher)

5.3 Exclusion Criteria:

- Participants with any other medical, behavioral, or developmental condition that in the opinion of the investigator may confound study data/assessments.
- Participants with planned extensive travel (more than 1 week) during the course of the 4-week intervention time period.
- Participants with deafness or blindness.
- Participants with known physical impairments affecting their ability to use their hands.
- Participants with active diagnosis of epilepsy and uncontrolled seizures.
- Participants whose age on the date of enrollment is outside the target age range.

6 Study Assessment

Parents who consent will be given access to the study device through its caregiver and child-facing smartphone app that provides therapeutic content. In order to access the study device app, parents will be provided access to two other apps. The first is Testflight. TestFlight is an online service for over-the-air installation and testing of mobile applications, currently owned by Apple Inc. that allows users to test iOS apps before they are released to the App Store. Parents will also be provided access to the Cognoa for Child Development app in order to create an account as a means to gain access to the study device app. The parents will only be able to engage with the study device app once they have created an account in the Cognoa for Child for Development app.

Parents will be instructed to use the study device with their child at home (not in public places) 4-6 times a week for 4 weeks. Parent report of the child's socialization will be measured at baseline (prior to starting to use the study device) and at the conclusion of the 4-week intervention period. Vineland-3 domain level caregiver report social skills and relationships will be administered over the phone by a trained research assistant or in an app. Usability metrics will also be collected by survey weekly (e.g. ease of use for child, frustration level, fatigue). Device usage, engagement, and progress metrics from the study device app will be collected throughout the study. Parent report of child's socialization will be collected using the Vineland-3 pre and post use of the study device. In addition, parents will fill out a Usability survey weekly throughout the study. These are the only 2 measures/surveys that parents fill out once enrolled in the study.

6.1 Training

The investigator and site research staff will be trained on the protocol and on all study procedures.

Monitoring of the site will occur to evaluate the progress of the study, verify the accuracy and completeness of data, assure that all protocol requirements, applicable FDA regulations and investigator obligations are being fulfilled and resolve any inconsistencies in the study records.

6.2 Usability Metrics

- Average duration of sessions using the device
- Total number of sessions completed
- Ratings of fatigue
- Ratings of frustration
- Ratings of irritability
- Ratings of comprehension of Instructions for caregivers
- Ratings of comprehension of Instructions for children
- Ratings of user app burdensome
- Ratings for the loading screen
- Ratings for the text to understand
- Ratings of video showing how to play first time

- Ratings of user free play

7 Data Collection and Storage

Data collection will be completed using electronic and/or paper report forms provided by Cognoa and data will be recorded into Cognoa dedicated study data repository.

Data fields will include:

- Date of ICF
- Participant demographics
- Device usage metrics
- VABS-3 caregiver report social skills and relationships domain answers and scores
- Usability metrics

The study data will be maintained in a secure location throughout the duration of the study. The pictures of the caregivers taken by the study participants will be stored in the device app, as well as on an Amazon S3 cloud server with secured access and SSL encryption.

Upon study completion or termination, records will be kept at a secure location until at least 2 years after the last approval of a marketing application and until there are no pending or contemplated marketing applications or at least 2 years have elapsed since the formal discontinuation of clinical development of the investigational product.

8 Adverse Events

8.1 Definitions

An **adverse event (AE)** is defined as untoward medical occurrence, unintended disease or injury, or untoward clinical signs (including abnormal laboratory findings) in subjects, device users or other persons, whether or not it is related to the investigational medical device. Expected adverse Device Events (ADEs) may be previously identified in nature, incidence, severity or outcome in the study protocol, informed consent document, device operator manual, other risk analysis documentation or regulatory application.

A **serious adverse event (SAE)** is any adverse event, whether related to the use of the investigational device or not, that:

- led to a death;
- led to a serious deterioration in the health of the subject that:
- resulted in a life-threatening illness or injury;
- resulted in a permanent impairment of a body structure or body function;

- required in-patient hospitalization or prolongation of existing hospitalization;
- resulted in medical or surgical intervention to prevent permanent impairment to a body structure or a body function;
- led to fetal distress, fetal death or a congenital abnormality or birth defect.

An **anticipated serious adverse device effect (ASADE)** is any SAE on health or safety or any life-threatening problem or death caused by, or associated with the device, if that effect, problem, or death was previously identified in nature, severity, or degree of incidence in the investigational plan, informed consent, operator manual, other risk analysis documentation or regulatory application; or any other serious problem associated with a device that relates to the rights, safety, or welfare of subjects.

An **unanticipated serious adverse device effect (USADE)** is any SAE on health or safety or any life-threatening problem or death caused by, or associated with the device, if that effect, problem, or death was not previously identified in nature, severity, or degree of incidence in the investigational plan, informed consent, operator manual, other risk analysis documentation, or regulatory application; or any other unanticipated serious problem associated with a device that relates to the rights, safety, or welfare of subjects.

In subjects, the ADEs/SADEs include the effects related to the investigational medical device (clinical study device), or the procedures involved. For device users or other persons (other clinical staff in the treatment room) ADE/SADE is restricted to the effects related to investigational medical devices. ADEs/SADEs may include the effects (1) resulting from insufficient or inadequate instructions for use, deployment, installation, or operation, or any malfunction of the investigational medical device; or (2) resulting from user error or from intentional misuse of the investigational medical device.

8.2 Recording AEs/ADEs and SAEs/SADEs

All reported AEs/SAEs or ADEs/SADEs will be: (1) evaluated and must be recorded in the participant's study case report forms (CRFs); (2) monitored and tracked from the time of the first treatment.

At each contact with the participant, the investigator must seek information on AEs/ADEs/SADEs by specific questioning and, as appropriate, by examination. AEs/ADEs/SADEs may be observed by the investigator and/or clinical research staff, elicited from the participant and/or family member or volunteered by the participant. All observed and volunteered adverse signs and symptoms, anticipated or unanticipated, regardless of severity or frequency, will be recorded in the case histories (medical chart and CRFs). Included in the descriptions should be the nature of the sign or symptom, the date of

onset, date of resolution (duration), the severity, anticipated or unanticipated, the relationship to study treatment or other therapy, the action taken (if any), and the outcome.

All SAEs/SADEs, anticipated or unanticipated, must be reported to Cognoa immediately but not later than 5 working days. The SADE must be recorded in: (1) the CRF and (2) a written report must be submitted to Cognoa within five (5) working days after the. Investigator first learns of the event and is to include a full description of the event and sequelae, in the format detailed by the Cognoa Serious Adverse Event Form.

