9.1 Potential Risks

Risks related to the study are expected to be minimal.

Physical risks for participating in the study are expected to be minimal. Children may experience some fatigue holding the device during intervention sessions. Children may also experience some irritation and frustration while using the device.

Caregivers/parents may feel some emotional discomfort from being asked or answering questions about their child's behavior.

Another potential risk is the possible release of sensitive medical, behavioral, or educational information. To mitigate the risk of releasing sensitive personal information, we adhere to confidentiality protocols to protect the privacy of personal information. When data is published, it is always anonymous and in a manner so that specific families or subjects cannot be identified.

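### Safety is a stated purpose, but active adverse-event questioning hangs on contacts that the schedule does not guarantee after first device use

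*Protocol*

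**What the plan says.** Section 2.1 of the protocol lists safety alongside effectiveness and usability as what the study is to evaluate. The objective in the Protocol Summary, Section 2 and the outcome list in Section 3 do not mention it.

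Section 8.1 defines an adverse event widely. It covers events "in subjects, device users or other persons, whether or not it is related to the investigational medical device".

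Section 8.2 says that reported events are "monitored and tracked from the time of the first treatment". It then sets the active step: "At each contact with the participant, the investigator must seek information on AEs/ADEs/SADEs by specific questioning and, as appropriate, by examination". Events that are observed or volunteered must also be recorded.

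The contacts themselves are fixed elsewhere:
- Section 5.1, before enrolment: "Eligibility will be determined during a scheduled phone call by Cognoa recruiters".
- Section 6, on the Vineland-3, given before first use and again at the end of the four weeks: it "will be administered over the phone by a trained research assistant or in an app".
- Section 6, during use: "Usability metrics will also be collected by survey weekly (e.g. ease of use for child, frustration level, fatigue" and so on. Section 6 adds that parents complete no instruments after enrolment other than the Vineland-3 and this survey.

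Section 9.1 expects possible fatigue, irritation and frustration in the child. For the adults it says: "Caregivers/parents may feel some emotional discomfort from being asked or answering questions".

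**The concern.** Section 8.2 reads as if written for a study with visits: it speaks of examination and medical charts. Section 6 describes home use of a phone app with surveys and no visits. A family that completes the final Vineland-3 in the app could finish everything scheduled after first use without anyone having asked about adverse events in general.

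At stake is the answer to the safety purpose. If few events are recorded, the reader cannot tell whether few occurred or few were asked about. An analysis plan cannot repair this afterwards, because events that were never elicited are not in the data.

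**Working it through.** The protocol gives no figure for event ascertainment, so there is none to reproduce. The check sets the schedule against the questioning rule and counts.

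**1. Which scheduled contacts fall after first treatment?**

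| Contact | Source | After first use? | Live? |
|---|---|---|---|
| Eligibility call | Section 5.1 | No | Yes |
| Consent | Section 10.1 | No | Form sent by email |
| Baseline Vineland-3 | Section 6 | No | Phone or app |
| Weekly usability survey | Section 6 | Yes | No, completed by the parent |
| Final Vineland-3 | Section 6 | Yes | Phone or app |

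Guaranteed live contacts after first use are 0 per family by app or 1 by phone, the latter with a research assistant. At the maximum enrolment of 30, that is 0 × 30 = 0 to 1 × 30 = 30 in the whole study. Unscheduled contacts may occur, but nothing in the plan secures them.

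**2. Do the listed instruments fill the gap?**

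Section 6.2 lists 12 metrics. Three are symptom ratings: fatigue, frustration and irritability (the last as "Ratings of irritability"). They match the child risks in Section 9.1. General adverse-event items: 0. Items naming caregiver discomfort: 0. Section 7 lists five data fields, and none is adverse events, although Section 8.2 does require reported events to go on the case report form.

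**3. Recall.**

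If the phone route is used, its single contact must cover 4 × 7 = 28 days. A weekly item would shorten this to about 7 days.

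**4. What one missed child is worth.**

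With n = 30, one affected child who is not recorded lowers the observed incidence by 1/30 = 3.3 percentage points. With fewer children enrolled, the figure is larger.

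**5. Illustration only.**

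Let s be the share of affected children whose event is captured. The protocol gives no value, so s is an assumption and is shown over a range. With zero events recorded in 30, the one-sided 95% upper bound on the true rate is (1 − 0.05^(1/30))/s = 0.095/s. For an event with an assumed true rate of 5%, the chance of recording at least one case is 1 − (1 − 0.05s)^30.

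| s | Upper bound, 0 of 30 recorded | Chance of at least one record, true rate 5% |
|---|---|---|
| 1 | 9.5% | 78.5% |
| 0.75 | 12.7% | 68.2% |
| 0.5 | 19.0% | 53.2% |
| 0.25 | 38.0% | 31.4% |

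The table shows only how the meaning of a clean safety record depends on s. It is not an estimate of the loss.

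**The case against.** The strongest reply is that Section 8.2 does not require a contact to be live. If a weekly survey or an app assessment counts, questioning is already mandatory four or five times per family, and the defect shrinks to an undefined term. This does not carry the point. Section 8.2 assigns the specific questioning to the investigator, and a usability survey that a parent fills in, with no listed adverse-event item, is not that. If the sponsor means the survey to count, Section 8.2 should say so.

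Other points stand in part:
- The survey form and the case report forms are not shown, and Section 6 gives the survey content only by example. The form may hold more than the protocol describes.
- Section 6.2 does not say whose fatigue, frustration or irritability is rated, so some caregiver symptoms may be covered. The caregiver discomfort in Section 9.1 comes from answering questions, and it is doubtful that mild discomfort of this kind would be an adverse event. The absence of an item for it is weak evidence taken alone.
- Expected risk is minimal, the expected child symptoms each have a corresponding weekly rating, and observed or volunteered events, including serious ones, must still be recorded and reported.
- The absence of safety from Section 3 is, taken alone, an editorial mismatch.

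These limits narrow the concern to events other than the rated symptoms. They do not supply a point after first use at which anyone is bound to ask about them.

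**Conclusion.** The concern holds, as a change that should be made rather than one that must be. Followed as written on the app route, the plan leaves events other than the rated symptoms to volunteered reports, which weakens the answer to Section 2.1. Under-counting is a risk, not a certainty, and its size cannot be derived from the protocol. Confidence is medium. The conclusion rests on reading investigator questioning as something a self-completed survey does not meet, and on the survey containing what the protocol describes. The study-wide counts assume full enrolment of 30.

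**What to change.** - Add one fixed open question to each weekly survey and to the week-4 assessment, whether by phone or app. For example: *any new or worsened health problem for child or caregiver since the last survey?*
- Have the investigator follow up every positive answer and record it on the case report form.
- State in Section 8.2 that these are the adverse-event collection points, and describe the added question in Section 6.
- Add a safety outcome to Section 3, such as the incidence of adverse events and adverse device effects, so that it matches Section 2.1.

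Assuming one survey a week for four weeks and 30 families, this gives 4 × 30 = 120 fixed prompts if the fourth survey coincides with the week-4 assessment, or 5 × 30 = 150 if they are separate.

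The cost is one item in a survey that parents already complete, one question at week 4, and short edits to Sections 3, 6 and 8.2. More minor events will be reported, and the investigator will spend a little time following them up. No visits are added, and Section 6's limit of two instruments can stand because the weekly item sits inside an existing survey.
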